6.6 Patient's profile

Eligibility for further treatment with Genotropin will be evaluated at the completion of assessment period for each booklet. If further treatment with Genotropin is not indicated, a major reason for treatment discontinuation should be selected from among the following options. If "Adverse event", "Laboratory abnormal", or "Death" is selected, relevant data should also be recorded in the adverse event section.

- [1] Reaching adult height (final height)
- [2] Reaching the standard height
- [3] Epiphyseal closure
- [4] Growth rate
- [5] Preference of patient/parent(s)
- [6] Non-compliance
- [7] Discontinuance of public funding

Ver.2

- [8] Change in diagnosis
- [9] Poor clinical response
- [10] Adverse event
- [11] Laboratory abnormal
- [12] Death
- [13] Lost to follow-up (specify "Names of center/department" if the reason for lost to follow-up is transfer to other hospital/department)
- [14] Others (the reason should be specified if "Others" is selected)

Treatment strategy as well as presence of other medication which has been switched to after discontinuation of Genotropin therapy should also be described for subjects completing or discontinuing Genotropin therapy.

6.7. Adverse events

Pertinent to safety assessment, the status of adverse events after the commencement of Genotropin therapy should be verified and the following information should be recorded. Adverse events should be verified in principle until the assessment period for each booklet is completed. Upon occurrence of any adverse event, the investigator shall provide appropriate intervention, promptly report to Sponsor in accordance with "Adverse event reporting" (Attachment 1), and follow up on the progress and outcome in principle until the symptoms disappear. Also, the investigator shall quickly notify Sponsor, "if a patient or the patient's partner conceives, or it has been found out that a patient or the patient's partner has conceived, whether adverse event has occurred or not," "if a serious adverse event occurred," and if any follow-up information thereto related has been obtained. Refer to "Adverse event reporting" (Attachment 1) for the details of procedures.

Furthermore, any occurrence of intrauterine exposure, or a serious adverse drug reaction or an adverse reaction not described in the package insert should be separately investigated as determined necessary by Sponsor.

- [1] Presence/absence of adverse event
- [2] Name of adverse event
- [3] Date of onset
- [4] Intervention
- [5] Seriousness
- [6] Outcome
- [7] Causal relation with Genotropin

[The following variables should be recorded if the adverse event is associated with abnormal test results, e.g., clinical laboratory]

- [8] Laboratory parameter

Ver.2

[9] Site reference

[10] Unit

[11] Date of measurement

[12] Result

Note: An adverse event is any untoward medical occurrence in a subject following Genotropin dose (including clinically significant change in laboratory test results); the event needs not necessarily to have a causal relationship with the treatment. A serious adverse event is any untoward medical occurrence that; Results in death; Is life-threatening (immediate risk of death), Requires inpatient hospitalization or prolongation of existing hospitalization; Results in persistent or significant disability/incapacity; Results in congenital anomaly/birth defect; or otherwise may result in medically important event or disorder.

6.8. Height follow-up after completion or discontinuation of Genotropin therapy

"Height Follow-up Form" will be used to collect data concerning body height in patients completing or discontinuing Genotropin therapy, and meeting the following criteria.

- Patients not switching to other drug product
- Patients not reaching adult height (final height)

[1] Date on which height follow-up is completed

[2] Height (to the first decimal place), and weight (to the first decimal place)

[3] Bone age

[4] Pubescence

[5] Future treatment strategy

Note: Any occurrence of adverse event during the height follow-up period should be separately investigated in details as determined necessary by Sponsor.

7. Analysis plan

Statistical analysis on safety and efficacy shall be performed; the results of which shall be posted in scientific journal, and reported at academic conferences and through research activities. In no event shall the investigator inquire Sponsor to perform statistical analysis for this investigation without confirming with Japan Genotropin Advisory Board in advance.

8. Discontinuation

8.1 Discontinuation of investigation

This investigation may be discontinued any time upon decision of the Investigator, or preference of the patient or the

Ver.2

patient's parent (or legally acceptable representative).

8.2 Discontinuation of treatment

Upon discontinuing Genotropin therapy, the Investigator shall record the reason for such discontinuation in the designated section of case report forms. The assessment at the termination (or discontinuation) of GH therapy should be appropriately performed.

9. Reporting and sharing of Investigation outcome

9.1 Reporting of Investigation outcome

Investigator and Sponsor hereby agree that the data obtained by Sponsor from this investigation shall be provided to regulatory authorities upon their request.

9.2 Sharing of Investigation outcome

(1) Patient feedback report

As a reference for the treatment strategy of each patient taking part in this investigation, Sponsor shall provide Investigator with a feedback report for each patient at every time case report forms are retrieved. Patient feedback report presents auxanologic data, bone age, adolescent development, hormone replacement, target and anticipated height, and other relevant information calculated based on data reported through case report forms, which are laid out in tables and figures.

(2) Public release (scientific journal, academic conference, and presentation, etc.)

Of the research results based on this investigation, the information publicly released by Sponsor shall be provided to each Investigator. Such public release includes but not limited to academic paper.

An Investigator may release his/her own academic report based on the data he/she contributed to this investigation or using the database; provided that the Investigator shall submit a copy or abstract of the report to Sponsor and obtain prior approval of Sponsor.

(3) Queries concerning database for this Investigation

The data compiled in the database for this investigation may be shared by Investigator in a Q&A format. Upon receiving an Investigator's question concerning treatment and diagnosis pertinent to the database for this investigation, Sponsor shall respond to the Investigator within approximately 1 month. The response to the question may be used by the Investigator as a reference to support day-to-day treatment and therapeutic plan for patients.

10. Ethical requirements

10.1 Declaration of Helsinki

Ver.2

This investigation shall be conducted in compliance with Declaration of Helsinki (Ethical Principles for Medical Research Involving Human Subjects; including the amendment thereto) which was adopted by the 18th General Assembly of the World Medical Association (Helsinki, Finland) in 1964.

10.2 Approval of institutional review board

Where the approval of institutional review board*² is required for conducting this investigation, the Investigator, prior to the commencement of this investigation, shall obtain a written document signed and dated by the institutional review board for approving this investigation including the patient information and consent form.

*² Institutional Review Board (IRB)/Independent Ethics Committee (IEC)

10.3 Data protection and patient's informed consent

Data concerning patients shall be handled with registration numbers and site ID. Investigator shall retain the patient identification log as required; provided that in no event shall Investigator disclose such information to any other person.

Before enrolling a patient to this investigation, the Investigator shall explain to the patient or his/her parent (or legally acceptable representative), verbally or in writing, the objective, contents, and that the patient or his/her parent (or legally acceptable representative) may discontinue this investigation any time they wish, and then shall obtain a written consent to take part in this study. Furthermore, a copy of such consent form shall be provide to the patient prior to enrollment, and the original consent form with signature shall be retained by the Investigator.

11. Others

11.1 Investigator and Japan Genotropin Advisory Board

(1) Investigator

Before taking part in this investigation, the Investigator shall review the protocol, enrollment form, and case report forms for this investigation, and shall be given Sponsor's adequate explanation on the objective and procedures of the investigation. Data collected for this investigation must be recorded in the case report forms by the Investigator.

(2) Japan Genotropin Advisory Board

Operation, organization, and management of this investigation shall be the responsibilities of Sponsor. Japan Genotropin Advisory Board is an organization comprising medical expertise selected by Sponsor, and its function is to provide its assessment and advice to Sponsor on the handling of data compiled for this investigation as well as the release of information contained in the database for academic papers, publications, and at academic conferences.

12. Amendment of this Protocol

Any change or amendment of procedures contained in this Protocol shall be reported to the institutional review board as required and/or in accordance with the on-site rules.

Ver.2

13. Contact for questions concerning this Investigation

PPD [REDACTED]

Post-marketing Surveillance Division, Development Japan, Pfizer Japan Inc.

Email address: PPD [REDACTED] _

14. Reference materials

Attachment: Adverse event reporting

Ver.2

1. REVISIONS FROM PREVIOUS VERSION

Version/ Date/ Author(s)	Summary of Changes/Comments
1.0/29-JUN-2015/PPD	Original version
2.0/27-OCT-2016/PPD	
5.2 Efficacy Analysis Set
 
The eligible criteria set was added.
 
8.2.1 Patient Summary
 
The case when the summary analysis results in the eligible criteria set were required was added.
 
8.2.2 Patient Characteristics and Treatment History
 
The case when the summary analysis results in the eligible criteria set were required was added.
 
New summary requirements were added to the “Treatment status of Genotropin.”
 
8.2.4 Efficacy Analysis
 
The case when the summary analysis results in the eligible criteria set were required was added.
 
8.2.4.1 Change in Height
 
The preparation of a new graph was added.
 
8.2.4.2 Change in Height SDS
 
The preparation of a new graph was added.

2. INTRODUCTION

This statistical analysis plan describes the statistical analysis plan for the special investigation (SGA long-term follow-up investigation) of Genotropin (hereinafter referred to as Genotropin). The texts drawn from the protocol are described using *italics* in this plan.

2.1. Study Design

Study Subjects

The indication for Genotropin in this investigation is as follows.

<Indication>

SGA (small-for-gestational age) dwarfism without epiphyseal closure.

Patient with the above disease who meet the following conditions will be enrolled in this investigation. In addition, the data in patients receiving Genotropin prior to the contract conclusion will also be included in this investigation.

- 1. Patients receiving Genotropin and consenting in writing to take part in this investigation.*
- 2. Newly enrolled patients who meet the following enrollment criteria.*
- 3. Patients who have already been enrolled in “Genotropin Special Investigation - Investigation of Genotropin long-term use in patients with SGA dwarfism without epiphyseal closure.”*

<Enrollment criteria>

Patients who meet all of the following criteria

- 1. Patients whose height and weight at birth are both below the 10th percentile for patients of the same gestational age, and at the same time, either body weight or height is less than -2 SD compared to patients of the same gestational age. Neonates whose body height at birth were immeasurable and thus were not measured will be evaluated with birth weight.*
- 2. Eligibility for the treatment*
 - 1. Patients must be not younger than 3 years.*
 - 2. The current body height must be less than -2.5 SD of the standard height.*
 - 3. A pre-treatment height velocity within 1 year prior to the commencement of treatment must be less than 0 SD.*
- 3. Patients whose poor physical growth after birth is attributable to disease other than intrauterine growth retardation cannot be enrolled in this investigation. Also patients who are currently receiving treatment that is known to cause poor physical growth cannot take part in this investigation.*

Assessment period

Assessment period for newly-enrolled patients

The fiscal assessment period of the year in which patient is enrolled will be defined as a period starting with the commencement of Genotropin therapy (which may be tracked back) and ending with the fiscal end. The fiscal assessment period of each subsequent year will be defined as the corresponding annual fiscal period.

Assessment period for ongoing subjects

For patients transferring from "Genotropin Special Investigation - Investigation of Genotropin long-term use in patients with SGA dwarfism without epiphyseal closure," the initial fiscal assessment period will be defined as a period starting on the day following the final assessment of data recorded in the last booklet for "Genotropin Special Investigation - Investigation of Genotropin long-term use in patients with SGA dwarfism without epiphyseal closure" and ending with the fiscal end of the applicable year. The fiscal assessment period of each subsequent year will be defined as the corresponding annual fiscal period.

For ongoing subjects, data collected during the "Genotropin Special Investigation - Investigation of Genotropin long-term use in patients with SGA dwarfism without epiphyseal closure" are included in the analysis set.

Height follow-up period

Patients completing or discontinuing Genotropin therapy will be followed up to document body heights from the completion or discontinuation of Genotropin therapy to the completion of investigation or until reaching adult height (final assessment). The follow-up period for each booklet will correspond to each fiscal year.

Target sample size

The target number of subjects from which data will be collected is approximately 400.

2.2. Objective

This investigation is intended to evaluate the long-term efficacy and safety of Genotropin in children with SGA dwarfism without epiphyseal closure. Responses of patients to Genotropin in relation to clinical conditions of patients, dose schedule, past history of growth hormone treatment, and other relevant factors will be investigated.

3. INTERIM AND FINAL ANALYSES

This investigation will perform interim analysis to consider the extension of the investigation period. Of the statistical analysis items specified in this plan, only those considered necessary will be analyzed at interim analysis. All the statistical analysis items specified in this plan will be analyzed at the final analysis.

4. HYPOTHESES AND DECISION RULES

4.1. Statistical Hypotheses

Since this is not a confirmatory investigation, statistical testing will be considered to be exploratory. The p value of test results will be evaluated as a descriptive statistic and no significance level will be specified, although ex-post threshold values may be set for screening.

4.2. Statistical Decision Rules

Not applicable.

5. ANALYSIS SETS

5.1. Safety Analysis Set

The safety analysis set is defined as the full analysis set that is as close to all the patients who received Genotropin as possible. Specifically, the safety analysis set is defined as a set of enrolled or reported patients from which those who meet any of the following conditions are excluded.

- a. Patients who violated the contract or for whom a defect was found in the contract (mentioned as “contract violation” and “defective contract” in the report).
- b. Patients who violated the enrollment criteria (mentioned as “enrollment violation” in the report).
- c. Patients for whom the dose of the product to be investigated has not been reported at all (mentioned as “no visit after the first prescription day” or “no dosing” in the report).
- d. Patients for whom no adverse event information has been reported at all (mentioned as “no adverse event information”).

The details of the criteria are according to the “Patient Enrollment Criteria to Analysis Sets and Guidance for Handling Data in Drug Use Survey.”

5.2. Efficacy Analysis Set

The efficacy analysis set is defined as a set of patients excluded those who meet the following condition from the safety analysis set.

- a. Patients who have not reported efficacy evaluation at all (mentioned as “No efficacy information” in the report).

Additionally, an eligible criteria set will be established to more specifically evaluate the efficacy of Genotropin from the viewpoint of the proper use of the product. The eligible patient set is defined as a set of patients excluded those who meet any of the following conditions from the efficacy analysis set.

- a. Patients aged less than 3 years old at the start of Genotropin.
- b. Patients whose height at the start of Genotropin is -2.5 SD or higher of the standard height.
- c. Patients for whom the height velocity in 1 year before the start of Genotropin is 0 SD or higher of the standard height velocity.
- d. Patients for whom the epiphyseal line is already closed at the start of Genotropin (bone age of 17 years or older for males and 15 years or older for females).

5.3. Other Analysis Sets

Set of patients who reached adult height (near final height).

The set of patients who reached adult height (near final height) is defined as a set of patients in the efficacy analysis set for whom adult height (near final height) was measured. Adult height (near final height) is defined as height after the time point that any of the following conditions is met.

- a. Annual height velocity of less than 2 cm after the maximum growth by puberty.¹
- b. Bone age of 17 years or older for males and 15 years or older for females.¹
- c. Reason for discontinuation in patient's profile of "reaching adult height (near final height)" or "epiphyseal closure".

Set of patients who did not reach adult height (near final height).

The set of patients who did not reach adult height (near final height) is defined as a set of patients in the efficacy analysis set who meet all the following conditions at the discontinuation of treatment and for whom height was measured at least once on Day 91 after the discontinuation of treatment or later.

- a. No puberty.
- b. Annual height velocity of 2 cm or higher after the maximum growth by puberty.
- c. Bone age of less than 17 years for males and less than 15 years for females.
- d. Reason for discontinuation in patient's profile of "reaching the standard height," "growth rate," "preference of patient/parent(s)," "non-compliance," "discontinuation of public funding," "change in diagnosis," "poor clinical response," "adverse event," "laboratory abnormal," or "others".

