Meanwhile, the data collected from this investigation shall be anonymized, compiled, and used as evidence for mechanisms and causes of poor physical growth in children with SGA dwarfism without epiphyseal closure, as well as response of such children to growth hormone treatment, and to facilitate new findings and discovery concerning poor physical growth in children.

1. Objective

This investigation is intended to evaluate the long-term efficacy and safety of Genotropin in children with SGA dwarfism without epiphyseal closure. Responses of patients to Genotropin in relation to clinical conditions of patients, dose schedule, past history of growth hormone treatment, and other relevant factors will be investigated.

2. Study subjects

The indication for Genotropin in this investigation is as follows.

<Indication>

SGA (small-for-gestational age) dwarfism without epiphyseal closure

Subjects with the above disease who meet the following conditions will be enrolled in this investigation. In addition, the data in patients receiving Genotropin prior to the contract conclusion will also be included in this investigation.

- [1] Patients receiving Genotropin and consenting in writing to take part in this investigation
- [2] Newly enrolled patients who meet the following enrollment criteria
- [3] Patients who have already been enrolled in "Genotropin Special Investigation - Investigation of Genotropin long-term use in patients with SGA dwarfism without epiphyseal closure."

<Enrollment criteria>

Patients who meet all of the following criteria

- 1) Patients whose height and weight at birth are both below the 10th percentile for patients of the same gestational age, and at the same time, either body weight or height is less than -2 SD compared to patients of the same gestational age. Neonates whose body height at birth were immeasurable and thus were not measured will be evaluated with birth weight.
- 2) Eligibility for the treatment
 - [1] Patients must be not younger than 3 years.
 - [2] The current body height must be less than -2.5 SD of the standard height.
 - [3] A pre-treatment height velocity within 1 year prior to the commencement of treatment must be less than 0 SD.

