8.2.4.2. Change in Height SDS

The summary statistics of measured values of height SDS at each age will be calculated for the efficacy analysis set and eligible criteria set. The evaluation points are according to [Appendix A1.1](#) Definition of timing for visit 1. The change in height SDS will be plotted with a solid line for individual male and female patients separately, with age on the horizontal axis and height SDS on the vertical axis. The start of treatment will be indicated as ▲, pubescence as ●, and reaching adult height (near final height) as ▼. They will be plotted with a dotted line after the completion/discontinuation of treatment.

The same calculation will be performed to prepare plots in the same manner for the set of patients who reached adult height (near final height) and set of patients not reached.

The summary statistics of measured values of height SDS at each evaluation point and change from the start of Genotropin will be calculated for a set of patients who reached adult height (near final height). The 95% confidence interval of the mean of the change will be calculated. The evaluation points are according to [Appendix A1.2](#) Definition of timing for visit 2. The change in height SDS will be plotted with a solid line for individual male and female patients separately, with evaluation points on the horizontal axis and height SDS on the vertical axis. The start of treatment will be indicated as ▲, pubescence as ●, and reaching adult height (near final height) as ▼. They will be plotted with a dotted line after the completion/discontinuation of treatment.

The summary statistics of measured values of height SDS at each evaluation point and changes from the start of Genotropin will be calculated in the efficacy analysis set and eligible criteria set. The 95% confidence interval of the mean of the change will be calculated. The evaluation points are according to [Appendix A1.3](#) Definition of timing for visit 3. The change in height SDS will be plotted with a solid line for individual male and female patients separately, with evaluation points on the horizontal axis and height SDS on the vertical axis. The start of treatment will be indicated as ▲, pubescence as ●, and reaching adult height (near final height) as ▼. They will be plotted with a dotted line after the completion/discontinuation of treatment.

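### SAP 5.3 lets a child whose bone age already meets the adult-height cut-off at the start of Genotropin count as having reached adult height, and the height SDS change in 8.2.4.2 does not screen such children out

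*SAP*

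**What the plan says.** Four parts of the SAP bear on this.

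- **Efficacy analysis set (5.2).** The only patients removed from the safety set are those described as "Patients who have not reported efficacy evaluation at all". Epiphyseal status plays no part.
- **Eligible criteria set (5.2 d).** This narrower set also drops "Patients for whom the epiphyseal line is already closed at the start of Genotropin", identified by a bone age of at least 17 years in boys and 15 in girls.
- **Adult-height set (5.3).** It "is defined as a set of patients in the efficacy analysis set for whom adult height (near final height) was measured". Adult height is "defined as height after the time point that any of the following conditions is met", and condition b is "Bone age of 17 years or older for males and 15 years or older for females". No condition refers to the start of Genotropin.
- **Height SDS to adult height (8.2.4.2, with the A1.2 visit windows).** The SAP states that the "change from the start of Genotropin will be calculated for a set of patients who reached adult height (near final height"). It does not limit this analysis to the eligible criteria set. For the same start-to-adult-height change in body weight SDS (8.2.4.5), BMI SDS (8.2.4.6) and IGF-I SDS (8.2.4.7), it does.

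**The concern.** The bone age that marks a child as closed at start in 5.2 d is the bone age that marks adult height in 5.3 b. A child who starts treatment at or above it can therefore belong to the adult-height set from the outset, with no treated growth behind the result.

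The start-to-adult-height change in height SDS is meant to describe what long-term treatment achieved. A child who met the end condition before or on the first dose adds a difference between two heights taken around the same date. If the gain in the other children is positive, each such child pulls the reported mean towards zero, and the 95% confidence interval is placed around that lower mean. The eligible criteria set would remove these children, and the SAP uses it for the three companion variables but not for this one.

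**Working it through.** The plan has no figure to reproduce here. The target of 400 is given without an effect size, SD or power, and this point does not depend on it. The check has three parts.

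**1. Set membership.** Take a child with bone age at or above 17 (boy) or 15 (girl) at start.

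| Step | Rule | Result for this child |
|---|---|---|
| Efficacy set | 5.2 a: some efficacy information | stays in |
| Eligible criteria set | 5.2 d: closed at start | removed |
| Adult-height set | 5.3 b: same bone-age cut-off, drawn from the efficacy set | in, if a height is measured |
| Height SDS change to adult height | 8.2.4.2: adult-height set | in |
| Weight, BMI and IGF-I SDS change to adult height | 8.2.4.5 to 8.2.4.7: adult-height set within the eligible set | out |

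**2. The two heights compared (A1.2).** The baseline window is day −90 to day 0. The adult-height window runs from the date of reaching adult height to 90 days later. The earliest value in each window is used.

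- Condition b met on day 0: the windows are [−90, 0] and [0, 90]. They share day 0. One height on day 0 can serve as both values, giving a change of exactly 0. The largest possible gap is 90 − (−90) = 180 days.
- Bone age read on day −30 (illustrative; Protocol 6.5 asks for pre-treatment results within 1 month before the start): the adult-height window is [−30, 60]. It overlaps baseline by 0 − (−30) = 30 days, so a pre-treatment height can be taken as adult height.

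If the word *after* in 5.3 is read strictly, a height on the same day as the bone-age reading would not count. A height taken between that reading and the first dose still could.

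**3. Effect on the mean and spread.** Let f be the share of the analysed children who were closed at start, D the mean change in the others, and d0 the mean change in those closed at start. Then

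observed mean = (1 − f) × D + f × d0, which is (1 − f) × D when d0 is about 0.

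The documents give neither f nor D. With an assumed D of 1.0 SD:

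| Assumed f | Observed mean (SD) |
|---|---|
| 0% | 1.00 |
| 2% | 0.98 |
| 5% | 0.95 |
| 10% | 0.90 |

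In counts, 1 child of 20 costs 5% of the mean, 2 of 50 cost 4%, and 5 of 50 cost 10%.

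For the spread, let s be the SD of the change in the other children and take every change in the closed group as 0. The variance is then (1 − f)s² + f(1 − f)D², which exceeds s² only if s² < (1 − f)D². With D = 1.0 and f = 0.05:

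- s = 0.7: 0.95 × 0.49 + 0.05 × 0.95 × 1 = 0.513, against 0.490, so wider.
- s = 1.0: 0.95 × 1 + 0.05 × 0.95 × 1 = 0.9975, against 1, so slightly narrower.

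No SD is given, so the direction is open.

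**The case against.** The strongest reply is that such children may not be in the data at all. The indication is "SGA (small-for-gestational age) dwarfism without epiphyseal closure", and SAP 5.1 b already removes "Patients who violated the enrollment criteria" before the efficacy set is formed. Conditions 5.2 a to c largely repeat enrolment criteria on age, height and height velocity, so 5.2 d may be one more safeguard and not a sign that closed children are expected. This stands in part: the presence of such children is not shown. It does not close the gap. The numbered enrolment criteria do not mention epiphyseal status, patients from the preceding investigation are listed as a separate entry category, and the guidance that details 5.1 is not in the documents.

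Second, belonging to the set is not the same as contributing to the mean. A child also needs a height in both A1.2 windows, and missing values are not imputed (SAP 7). This stands, and it may lower f.

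Third, much would be visible anyway. Baseline bone age is tabulated by these cut-offs (8.2.2), exclusions from the eligible set are listed with reasons (8.2.1), and individual plots mark start and adult height. The height SDS change is also reported in the eligible set at yearly points, at completion of treatment and at completion of height follow-up (8.2.4.2, A1.3). That helps a reader detect the problem, but no planned summary gives the start-to-adult-height change in height SDS without these children.

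Finally, low numbers at enrolment need not mean a low share in this set. Closed children qualify at once, whereas children who start young need years to do so.

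**Conclusion.** The point holds as a gap in the definitions. SAP 5.3 allows adult height to be reached at or before the first dose, and 8.2.4.2 lacks the restriction that its companion analyses carry. Any such child with both heights recorded adds a change near 0, and the mean falls by the proportion f. The size is unknown: zero if no such child is analysed, and 2% to 10% of the gain over the illustrative shares above.

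Three stronger readings are tempting, and the documents do not support them.

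- A reader might infer that closed children do enter and do dilute the result. The text shows only that they can.
- A reader might infer that the confidence interval must widen. The effect on the spread depends on an SD that is not given.
- A reader might take this to undermine the investigation's main efficacy result or all the adult-height analyses. The visible endpoint list (6.2) names no primary endpoint, the testing is exploratory (4.1), and the start-to-adult-height changes in weight, BMI and IGF-I SDS are already protected.

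The conclusion assumes that d0 is about 0. This follows from the SAP's own equation of these bone ages with closure and from the 180-day limit on the gap when condition b is met on day 0. It also rests on the visible text; 8.2.4.9 is blacked out.

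**What to change.** Either of two changes is enough.

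1. In 5.3, add one sentence: *the adult-height condition must be first met after the start of Genotropin; patients who meet it at or before the start are not in this set.*
2. In 8.2.4.2, report the start-to-adult-height change in height SDS in the eligible criteria set, instead of or alongside the present analysis, as 8.2.4.5 to 8.2.4.7 do.

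With either, state how many patients were excluded for closure at start. The baseline bone-age table in 8.2.2 already supplies the information, so no new data are needed.

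The cost is one sentence and possibly a few patients fewer in this analysis. The first change alters a set that is also used in 8.2.4.1 and 8.2.4.5 to 8.2.4.7. The second leaves 5.3 alone, but as a replacement it may also drop patients excluded by 5.2 a to c. Reporting both sets side by side avoids that loss.
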